STUDY PROTOCOL

Title: The Effect of Using Crochet Octopus in Reducing The Pain Developed During The Process of Heel Lance In Neonates: A Randomized Controlled Study

NCT number: 04560374

Document date: May 1, 2020

Objectives: The main objective of this study was to determine the effect of using a crochet octopus to reduce acute pain that develops during a heel lance in neonates.

Design: This study used a randomized controlled design.

Methods:

Participants: Neonates born between May 1, 2020, and August 15, 2020, were included in the study. The study was conducted at a well-child unit in a research and training hospital with healthy, term neonates. The neonates were not hospitalized during the research. All blood samples for the Guthrie test were routinely taken at the well-child unit in this hospital.

Measurements: Descriptive data of participant neonates were documented in the neonatal identification form using hospital records. The pain score measured with Neonatal Infant Pain Scale.

Intervention: The crochet octopus was delivered to the hands of the neonates in the experimental group 10 min before the heel lance process occurred, and the neonates were in contact with the crochet octopus for up to 10 min after the procedure (Figure 3). In this procedure, the neonates were dressed. The procedure was carried out under a radiant heater in baby mode, and neonates were placed in a supine position. A pulse oximeter device was used

to monitor oxygen saturation and heart rate. The device probe was attached to the neonates' wrists during the time under the radiant heater. The respiratory rate was counted by one researcher for 1 min. The body temperature was measured by researcher with an infrared thermometer. The observation form was completed before the procedure began (0th min). No intervention was performed beforehand to better draw the heel blood, and the blood was drawn from the left heel for each neonate because of the researcher's holding position. A fine lancet was used for heel lancing; before the procedure, the heel was wiped with 70% isopropyl alcohol wipes in a circular motion and then wiped with dry cotton. Blood was drawn from the heel while the neonate was on the mother's laps. The observation form was completed again during the procedure and after the procedure (at 2nd and 10th min).

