The total data collection time took an average of 20 min, and the entire process was recorded on video. After the process, researcher performed the heel lance procedure with video recording. After the procedure was completed, video recordings were assessed by two observers—a neonatal nurse specialist and researcher—together to eliminate bias. Neonatal durations of crying and NIPS scores were calculated at 0 min (before the procedure) and at 2nd and 10th min after the process, and the scores were recorded on the data collection form. During the procedure, neonates remained with the mothers. Neonates who cried before the procedure were held by mothers until they calmed down; approximately 15 min later, they could be included in the study.

Before collecting the data, 50 crochet octopus were crocheted by three researchers according to the standards noted in the Methods' Instruments section. A new crochet octopus was used for each neonates during the heel lance procedure; the octopus was then washed in a washing machine with an organic detergent for neonates in 60°C (hot) water.

The control group of neonates underwent the heel lance process without a crochet octopus.

Ethical Considerations: Ethical approval was obtained from the Clinical Researchers Ethical Committee of Giresun University (Approval No. 06.02.2020/20). Institutional permission was obtained from the Public Hospitals Association of Giresun. In addition, parents of the neonates were asked for written informed consent forms for the data collection, procedure, and video recording.

Statistical Analysis Plan

The Number Cruncher Statistical System (NCSS 2007; Kaysville, UT, USA) was used for statistical analysis. Descriptive statistical methods (average, standard deviation, median, quartiles, frequency, rate, minimum/maximum) were used to assess relevant data. Normal distribution characteristics of the study parameters were examined with the Kolmogorov-Smirnov test. Heart rate, oxygen saturation, and body temperature had normal distributions, but respiratory rate, duration of crying, and NIPS pain scores did not have normal distributions. The independent *t*-test was used for the cross-group comparison of variables with normal distributions, and the Mann-Whitney *U* test was used for those without normal distributions. Cohen's kappa coefficient was calculated for the interrater reliability of observers. Significance was assessed in the range of 95% reliability.

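### The SAP plans tests and descriptive summaries but no between-arm effect estimate with a confidence interval, so the size and precision of the effect on pain are not planned to be reported

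*Combined protocol and SAP*

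**What the plan says.** The Objectives paragraph of the protocol says the study is to "determine the effect of using a crochet octopus to reduce acute pain that develops during a heel lance in neonates". On the measure, Measurements says: "The pain score measured with Neonatal Infant Pain Scale". The procedure text before the SAP gives the timing: "Neonatal durations of crying and NIPS scores were calculated at 0 min (before the procedure) and at 2nd and 10th min after the process".

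The Statistical Analysis Plan is one paragraph. It reports that "respiratory rate, duration of crying, and NIPS pain scores did not have normal distributions", and for the between-group comparison that "the Mann-Whitney *U* test was used for those without normal distributions". Heart rate, oxygen saturation and body temperature go to an independent t-test. The summaries listed are mean, SD, median, quartiles, frequencies, rates and extremes; the plan does not say whether they are given by arm. Cohen's kappa is listed for agreement between the two observers. The paragraph closes: "Significance was assessed in the range of 95% reliability".

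Neither the protocol nor the SAP states a sample size, power, target difference or smallest important difference.

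**The concern.** A question about the effect of an intervention needs an answer in two parts: how large the difference between arms is, and how precisely it is known. The planned between-arm inference supplies neither. As specified, the U test on NIPS and crying yields a p-value. A small p-value says that the arms differ without saying by how much. A large one says only that a difference was not shown.

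The second case carries the greater risk. With no interval and no stated target difference, a non-significant result could be reported as absence of benefit when the data are merely too few to tell.

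**Working it through.** **Step 1. Does the SAP name an effect estimate anywhere?** Taking its elements in turn:

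| Element of the SAP | Between-arm effect size? | Precision of that effect? |
|---|---|---|
| Descriptive statistics | No difference named; not stated to be by arm | No |
| Kolmogorov-Smirnov test | No, checks distribution | No |
| Independent t-test | Not named; test only | Not named |
| Mann-Whitney U test | Not named; test only | Not named |
| Cohen's kappa | No, concerns the raters | No |
| Closing sentence on significance | No | No; the 95% is attached to significance |

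Nothing in the paragraph commits the trial to a treatment-effect estimate or an interval. The plan gives no figure of its own to reproduce.

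**Step 2. What could a p-value alone leave open?** This is an illustration. The documents give no arm size, so *n* per arm is an assumption, shown over a range; the 50 octopuses made are not a stated sample size. Equal arms and two-sided 5% are also assumed.

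- 95% half-width for a difference in SD units: 1.96 × √(2/n).
- Difference detectable with 80% power: (1.96 + 0.84) × √(2/n).
- Let θ be the probability that an octopus infant scores lower than a control infant, ties counted half. Without ties, the U test reaches p<0.05 once θ departs from 0.5 by 1.96 × √((2n+1)/(12n²)).

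| Assumed n per arm | Half-width (SD) | Detectable at 80% power (SD) | θ departure for p<0.05 |
|---|---|---|---|
| 25 | 0.55 | 0.79 | 0.16 |
| 40 | 0.44 | 0.63 | 0.13 |
| 50 | 0.39 | 0.56 | 0.11 |
| 75 | 0.32 | 0.46 | 0.09 |

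Example at n = 50: 1.96 × √(2/50) = 1.96 × 0.2 = 0.39, and 1.96 × √(101/30,000) = 1.96 × 0.058 = 0.114.

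**Step 3. Reading the table.**

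- *Non-significant, n = 50.* If the observed difference is zero, the interval is about −0.39 to 0.39 SD. If it falls just short of significance, the interval runs from about 0 to 2 × 0.39 = 0.78 SD. Both would be reported as not significant, yet they carry different messages.
- *Just significant, n = 50.* An observed θ of 0.5 + 0.114 = 0.614 has an approximate interval of 0.50 to 0.614 + 0.114 = 0.73. The p-value alone does not show that this spans almost no effect to a sizeable one.

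**Step 4. Sensitivity to ties.** Ties shrink the standard error under no effect. If two-thirds of all scores shared one value (an assumption, with the rest untied), the half-width at n = 50 becomes 0.114 × √(1 − (2/3)³) = 0.114 × 0.84, about 0.095. The no-ties θ column is therefore an upper-end figure. Step 1 does not depend on it.

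**The case against.** The strongest reply is that the descriptive statistics already do much of this work. If means and SDs are reported by arm, a reader can see the direction and rough size of any difference. With the arm sizes, an approximate interval follows from (difference in means) ± 1.96 × √(s₁²/n₁ + s₂²/n₂). This largely stands. A reader might infer from the missing interval that neither a significant nor a null result could be interpreted at all; the documents do not support that, because the listed summaries go beyond a p-value. Two limits remain: the SAP does not say the summaries are by arm, and an interval a reader works out afterwards is not a pre-specified estimate on which the trial bases its conclusion.

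A reader might also infer that NIPS is bunched near zero, so that medians would often coincide despite a significant U test. The documents give neither the scale's range nor any score distribution, so that rests on assumption. Even if it were so, means and quartiles are also planned and could show a difference that the medians hide.

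Finally, the missing sample size and target difference are a separate gap that an interval does not fill, and the choice among estimates is partly preference. Both points are fair. An interval does, however, show how much information the trial actually obtained.

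**Conclusion.** The concern holds in this form: the objective is to determine an effect, and the SAP specifies descriptive summaries and hypothesis tests but no between-arm estimate or confidence interval for any outcome. This rests on the text alone. Followed as written, the plan does not provide for reporting the size and precision of the effect. A non-significant p-value could not be told apart from too little information, and by-arm summaries would give only direction and rough size.

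How much this matters depends on arm sizes that the documents do not state. At an assumed 25 to 50 per arm, half-widths of about 0.55 to 0.39 SD would go unreported. These use a normal approximation and illustrate scale only.

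This is a cheap improvement that should be made. It does not invalidate the planned tests.

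**What to change.** Add to the Statistical Analysis Plan:

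1. For NIPS and crying duration at the analysed post-procedure times (2 and 10 min), report one between-arm estimate with a 95% CI alongside the U test. Two suitable choices are θ with a Brunner-Munzel interval, or the difference in means with a bootstrap interval. One is enough, but name it.
2. For the t-test variables, report the mean difference with a 95% CI.
3. State that summaries are given by arm.
4. State that conclusions rest on the estimate and its interval, and that absence of effect will not be concluded from p>0.05 alone.

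The SAP already reports which variables departed from normality, so the data may have been examined. If the change is made after the data are seen, label it as an addition to the plan.

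The cost is SAP wording and a few lines of analysis and reporting. No new infants, measurements or procedures are needed.
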